## 1.0 OBJECTIVES

### Primary Objectives

#### Arm 1

- To estimate the efficacy of TRC102 and temozolomide, as measured by response rate, in bevacizumab naïve glioblastoma

#### Arm 2 (opens only if Arm 1 meets efficacy criteria)

- To estimate the efficacy of TRC102 and temozolomide, as measured by response rate, in bevacizumab refractory glioblastoma

### Secondary Objectives

1. Evaluate the toxicities of oral TRC102 and temozolomide in this patient population
2. Estimate the efficacy of TRC102 and temozolomide, as measured by progression-free survival, progression-free survival at 6 months and overall survival, in bevacizumab naïve glioblastoma
3. Estimate the efficacy of TRC102 and temozolomide, as measured by progression-free survival in bevacizumab refractory glioblastoma

### Exploratory Objective

- Assess the tissue correlates of methylpurine DNA-glycosylase (MPG) and topoisomerase II $\alpha$  (Topo II $\alpha$ ), and O-methylguanine DNA methyltransferase (MGMT) status, with response, PFS, and overall survival

## 2.0 BACKGROUND AND RATIONALE

### 2.1 Glioblastoma

Although the recent addition of temozolomide (TMZ) to radiation therapy for the treatment of glioblastoma (GBM) has resulted in improved outcomes, the estimated 2-year survival with maximal therapy remains only 27% (Stupp 2005, Stupp 2009). Almost all GBMs progress, with a median time to progression of approximately 7 months. The prognosis is very poor for patients who have progressive/recurrent GBM. There is currently no standard therapy for recurrence. Salvage chemotherapies are largely ineffective, with progression-free survival at 6 months (PFS6) rates of 10-15%. Bevacizumab therapy at recurrence is associated with a high response rate, but not significantly increased survival. Survival after failure of bevacizumab administered for GBM recurrence is very poor with a median survival of 4-6 months and PFS 6 of 0 (Reardon 2012). Hence, new therapies for recurrent GBM are urgently needed.

### 2.2 TRC102

An NCI phase I study of TRC102 and temozolomide in relapsed solid tumors and lymphomas evaluated the safety of the combination of TRC102 and temozolomide (P9483, NCT01851369). Based on this dose escalation trial, the recommended doses for the phase II study are 150mg/m^2 for temozolomide and 150mg flat dose for TRC102. No dose limiting toxicity was seen at 150mg/m^2 of temozolomide and a TRC102 dose of 150mg administered days 1-5 of a 28-day cycle (personal communication, [name]). We propose to evaluate efficacy of TRC102 at 150mg flat dose combined with TMZ 150mg/m^2 in a phase II trial of recurrent GBM.

We hypothesize that oral TRC102 can be safely administered with TMZ and that it will potentiate DNA damage caused by TMZ, resulting in increased tumor response and improved survival as compared with historic controls. A dose escalation trial of intravenous TRC102 in combination with TMZ has been performed in relapsed systemic and central nervous system tumors at Case Comprehensive Cancer Center. A variety of dose-intense schedules of TMZ at recurrence have been evaluated. As compared with the standard 5 days every 28 days schedule, the dose- intense regimens have not shown greater efficacy and are associated with increased incidence and severity of lymphocytopenia (Weller 2013.). Therefore, we selected the standard schedule of TMZ.

We hypothesize that biologic markers obtained in tumor tissue collected at the time of tumor progression will correlate with treatment response. N-methylpurine DNA glycosylase (MPG) overexpression, together with inhibition of base excision repair (BER), sensitizes glioma cells to TMZ (Tang 2011). As an exploratory aim, we propose to determine expression of MPG by IHC in resected tumor tissue from initial diagnosis, and correlate this with treatment response, a design similar to the study of Weeks et al (Weeks 2013) in which expression of uracil-DNA glycosylase in lung cancer was found to correlate with pemetrexed response. Because overexpression of topoisomerase 2a

(topo2a) correlates with increased sensitivity to the TRC102 potentiation of cytotoxicity of DNA damaging agents, we propose to determine expression of topo2a in resected tumor tissue and correlate its expression with treatment response. O-methylguanine DNA methyltransferase (MGMT) is a strong predictor of response to TMZ. MGMT methylation status will be collected to correlate response with TMZ, independent of TRC102 co-administration.

### **Resistance to TMZ**

A major obstacle to effective treatment with TMZ in GBM is the presence of elaborate mechanisms of DNA repair. For instance, TMZ forms O-methylguanine (OmG), 7-methylguanine (NmG), and 3- methyladenine (NmA) DNA adducts that are repaired by at least two mechanisms. The OmG DNA adduct, a cytotoxic and genotoxic lesion, is repaired by MGMT. MGMT activity is a major mechanism of resistance to methylating agents. In contrast, cell death caused by OmG adducts is promoted by mismatch repair (MMR) system, such that deficiency in MMR is associated with pronounced resistance to methylating agents. NmG and NmA DNA adducts are removed by the BER pathway (Liu 1999, Liu 2002).

### **Base excision repair (BER) pathway**

BER is an important drug resistant factor because it recognizes a variety of substrates and has the ability to rapidly and efficiently repair NmG and NmA DNA adducts. BER is the major pathway that protects cells against the potentially harmful effects of spontaneously and chemically occurring DNA damage, including (i) inappropriate bases; (ii) abasic sites that are formed by enzyme-catalyzed, spontaneous or chemical-induced base release; and (iii) DNA single strand breaks produced during the processing of damaged DNA. Efficient BER minimizes the impact of these lesions in normal and tumor cells. Thus, when BER is disrupted, these abundant N-methylated DNA adducts and intermediates generated in the repair process become highly cytotoxic. Most importantly, BER disruption is able to bypass other resistance factors such as MMR defects and high MGMT activity.

Base excision repair efficiently repairs DNA bases through a series of enzymatic steps, starting with the action of a glycosylase to excise the damaged base. TRC102 interrupts this process because TRC102 binds to the apurinic site created through the action of the glycosylase, thereby interrupting normal repair. As well, TRC102 bound DNA is a substrate for topo IIa which results in DNA strand breaks that then trigger cellular apoptosis.

### **Introduction to TRC102**

TRC102 (NSC-3801), a biochemical inhibitor of the BER pathway developed and studied by investigators from Case Comprehensive Cancer Center (CCCC), Cleveland Ohio, reverses TMZ resistance in preclinical models at doses that are well tolerated. The ability of TRC102 to interrupt the BER pathway was demonstrated *in vitro* (Yan 2007).

Pharmacology studies demonstrated its ability to inhibit BER induced by treatment with alkylating agents, including TMZ, and anti-metabolite chemotherapy. When administered with TMZ, TRC102 covalently binds to apurinic/apyrimidinic (AP) sites generated by DNA glycosylase, in an attempt to replace DNA bases damaged by TMZ. TRC102-bound AP sites are refractory to the catalytic activity of the apurinic/apyrimidinic endonuclease (APE), leading to the interruption of BER.

Available data support the hypothesis that TRC102-bound DNA is a substrate for topo II, which cleaves TRC102-bound DNA sites to produce strand breaks in cancer cells that cause cellular apoptosis.

As a result, TRC102 is able to potentiate the activity of TMZ (and other chemotherapeutics that activate the BER pathway) in cancer cells that express high levels of topo II (both *in vitro* and *in vivo*), without increasing toxicity in non-cancer cells (i.e., bone marrow cells) that express low levels of topo II.

### **Activity of TRC102 in Combination with Alkylating Chemotherapy**

The ability of TRC102 to potentiate chemotherapy was initially demonstrated using TMZ (Li 1999, Liu 2002, Taverna 2001). Collectively, the available data indicate that treatment of cancer cells with TMZ produced N-methylguanine and N-methyladenine DNA adducts that activated BER to generate AP sites within double-stranded DNA. TRC102 bound covalently to AP sites to form structurally modified AP sites that were then resistant to the repair activity of APE. The persistence of these lesions led to cell death through the generation of DNA strand breaks.

The lethal toxicity induced by TMZ combined with TRC102 appears to be mediated through the poisoning effect of topo II. While TRC102-bound AP sites are refractory to the catalytic activity of APE (indicating their ability to block BER), they are cleaved by purified topo II or nuclear extracts from tumor cells expressing high levels of topo II, suggesting that TRC102-bound AP sites stimulate topo II-mediated DNA cleavage.

Furthermore, cells treated with TMZ and TRC102 demonstrate increased expression of topo II and increased formation of  $\gamma$ -H2AX foci (a marker of DNA double strand breaks) that co-localizes with up-regulated topo II. The cleavage of TRC102-bound AP sites by topo II also explains the ability of TRC102 to potentiate the effects of TMZ in cancer cells (that have high levels of topo II) compared to normal cells (which have low levels of topo II). For example, *in vitro* addition of TRC102 effectively sensitized tumor cells, but not bone marrow cells, to the effects of TMZ.

Several preclinical studies have demonstrated improved therapeutic efficacy of alkylating agents by blocking BER with TRC102. *In vivo* studies have shown that TRC102 potentiates the antitumor effect of TMZ in human tumor xenografts in nude mice. Mice carrying SW480 tumor (AGT expressing, MMR wt and p53 mutant) that were resistant to treatment with TMZ alone had cessation of tumor growth lasting  $50 \pm 13$  days and very slow regrowth when treated with TRC102 (2 mg/kg) plus TMZ (120 mg/kg), yielding tumor growth delays of  $70 \pm 14$  days ( $p < 0.002$ ) compared with untreated tumors. Tumor

[figure not shown]
regression following treatment with TMZ and TRC102 treatment reflected DNA strand breaks and a significant increase in tumor apoptosis. Therefore, TRC102 inhibition of DNA BER is a promising strategy to sensitize tumor cells to therapeutic alkylating agents.

In the first in human phase I clinical trial, TRC102 was administered as a 5-day intravenous continuous infusion based on animal data. Dosing started at 15 mg/m^2 TRC102 daily for 5 days and plasma samples were collected and analyzed for TRC102 using validated methods. Pharmacokinetic parameters were derived using a single compartment intravenous infusion model and plasma TRC102 concentrations from 5 patients across 15 dosing cycles. Pharmacokinetic studies demonstrated an unexpected prolonged half-life of TRC102, estimated to be 45 hours (range: 32.1 - 68.8 hours) which represents a 10-fold increase when compared to the TRC102 half-life observed in dogs ( $t_{1/2} = 4.5$  hours) and a 143-fold increase when compared to the half-life observed in rats ( $t_{1/2} = 19$  min). The volume of distribution (Vss) was estimated to be 1,437 L and the clearance (CL) was estimated to be 22.47 L/h. The Cmax (across all patients) was 41.4 ng/mL. Individual pharmacokinetic exposures and derived PK parameters demonstrated very little intra- and interpatient variability. (Savvides (a) abstract) The protocol was therefore revised with TRC102 administered as one hour continuous infusion. The average half-life of TRC102 at this schedule was 55.04 hours (range: 12.2 - 100.3 hours, n = 20), statistically not different from half-life of TRC102 administered as a five-day continuous infusion (Savvides (b) abstract).

Subsequently PK of the oral formulation of TRC102 was assessed in a phase I study of TRC102 and pemetrexed in advanced solid tumors. TRC102 was administered as monotherapy on days 1 to 4 of a two-week cycle. Plasma for PK parameters was collected prior to dosing and 5, 15, and 30 minutes, and one, 2, 3, 4, 6, 8, and 24 hours following the first and fourth doses of TRC102. The overall mean half-life of 28 hours was unchanged with increasing doses or cycle and the exposure increased proportionally with dose. The target AUC was exceeded in all patients who received at least 4 doses of TRC102. TRC102 accumulated with daily, dosing. The target Cmax of 50 ng/mL for in vivo activity was achieved by the fourth daily dose in 2 of 3 patients at 15 mg/M/day and in all patients receiving 30 mg/M/day and higher doses. The variability and PKs between patients were significantly influenced by both gender and baseline serum creatinine (Gordon 2012).

Pharmacodynamic markers, including analysis of AP sites measured on DNA extracted from patients' mononuclear cells (PBMCs) as well as DNA strand break determined by comet assay at multiple time points were obtained in the Phase I clinical trial of TRC102 and TMZ. PD results, performed on 22 patients, showed that administration of the combination of TMZ and TRC102 resulted in 10-40% reduction in detectable AP sites. Comet assay results, performed on 20 patients revealed that the combination of TMZ and TRC102 2 to 3-fold higher levels of DNA strand breaks compared to TMZ alone (Savvides (a) abstract).

resulted in further expansion to 10 evaluable patients, with no additional DLTs observed. No DLTs have been observed in Arm B. The best response in Arm B is partial response in one patient with GBM and stable disease in head/neck squamous cell brain metastasis, off treatment for 24 months.

### **2.3 Rationale**

TRC102 reverses TMZ resistance in preclinical models at doses that are well tolerated. When administered with TMZ, TRC102 covalently binds to apurinic/apyrimidinic (AP) sites which are generated by DNA glycosylase in an attempt to replace DNA bases damaged by TMZ. TRC102-bound AP sites are refractory to the catalytic activity of the apurinic/apyrimidinic endonuclease (APE), leading to the interruption of BER. Moreover, TRC102-bound DNA causes topoisomerase II dependent DNA strand breaks that induce apoptosis. TRC102 is selective for rapidly dividing cancer cells as these cells express higher levels of topoisomerase II compared with normal cells. Therefore we propose a trial of TMZ and TRC102 in patients with recurrent GBM who have failed prior TMZ.

### **3.0 PATIENT ELIGIBILITY CRITERIA**

#### **3.1 Patient Sample**

Sample Size:

Arm 1: 31 bevacizumab-naïve patients

Arm 2: 35 bevacizumab-refractory patients

Accrual Rate:

4-5 patients per month

Gender:

Male and female

Age:

Patients must be at least 18 years of age.

Race:

Minorities will be actively recruited. No exclusion to this study will be based on race or ethnicity.

#### **3.2 Eligibility Criteria**

1. Patients must have histologically confirmed glioblastoma that is progressive or recurrent following radiation therapy and temozolomide.
2. Tumor MGMT methylation status must be available. Results of routinely used methods for MGMT methylation testing (e.g. MSPCR or quantitative PCR) are acceptable.
3. Arm 1 patients must have measurable (defined by at least 1 cm x 1 cm) contrast-enhancing disease by MRI imaging within 21 days of starting treatment.
4. Patients must be able to undergo MRI of the brain with gadolinium. Patients must be maintained on a stable or decreasing dose of corticosteroid regimen (no increase for 5 days) prior to this baseline MRI.

5. Arm 1 patients must be in first recurrence of glioblastoma following radiation therapy and temozolomide.  
Arm 2 patients may have an unlimited number of prior therapy regimens but may not have received prior antiangiogenesis therapy except for bevacizumab (patients may not have received afibbercept, ramucirumab, cediranib, cabozantinib, or XL184).
6. Arm 1 patients must have not received bevacizumab previously.  
Arm 2 patients must have progressed/recurred on bevacizumab as the most recent regimen. Patients on Arm 2 should continue on bevacizumab as clinically necessary to control brain edema.
7. Patients must have a tumor tissue form indicating availability of archived tissue from initial resection at diagnosis of glioblastoma completed and signed by a pathologist. See Section [9.5.1](#). Availability of tissue is not a requirement for study participation.
8. Patients must have recovered from severe toxicity of prior therapy. The following intervals from previous treatments are required to be eligible:
  - 12 weeks from the completion of radiation
  - 6 weeks from a nitrosourea chemotherapy
  - 3 weeks from a non-nitrosourea chemotherapy
  - 4 weeks from any investigational (not FDA-approved) agents
  - 2 weeks from administration of a non-cytotoxic, FDA-approved agent (e.g., erlotinib, hydroxychloroquine, etc.)
9. Patients must be 18 years of age or older.
10. Patients must have a Karnofsky Performance Status  $\geq 60\%$  (i.e. the patient must be able to care for himself/herself with occasional help from others).
11. Patients must have the following organ and marrow function:
 

Absolute neutrophil count	$\geq 1,500/\text{mcL}$
Platelets	$\geq 100,000/\text{mcL}$
Hemoglobin	$\geq 9 \text{ g/dL}$
Total bilirubin	$\leq$ institutional upper limit of normal
AST (SGOT)/ALT (SGPT)	$\leq 4 \times$ institutional upper limit of normal
Creatinine	$\leq$ institutional upper limit of normal
OR	
Creatinine clearance	$\geq 60 \text{ ml/min}/1.73\text{m}^2$ for patients with creatinine levels above institutional normal
APTT or PTT	$\leq 1.5 \times$ institutional upper limit of normal
12. Patients must be able to provide written informed consent.

13. Women of childbearing potential must have a negative serum pregnancy test prior to study start. Women of childbearing potential and men must agree to use adequate contraception (hormonal or barrier method of birth control; abstinence) prior to study entry, for the duration of study participation, and through 30 days after the last dose of study drug. Should a woman become pregnant or suspect she is pregnant while participating in this study, she should inform her treating physician immediately. Men treated or enrolled on this protocol must also agree to use adequate contraception prior to the study, for the duration of study participation, and through 30 days after the last dose of study drug.
14. Patients must have no concurrent malignancy except curatively treated basal or squamous cell carcinoma of the skin or carcinoma in situ of the cervix, breast, or bladder. Patients with prior malignancies must be disease-free for  $\geq$  five years.
15. Patients must be able to swallow capsules.

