#### **4.2 Treatment Requirements**

All eligible patients who consent to this study must have a baseline (post-operative, if surgery is applicable) pre-treatment MRI. This baseline scan must be done within 21 days prior to the initiation of treatment.

Prior to every cycle patients must have:

- 1) ANC  $\geq$  1500/ $\mu$ l and platelets  $\geq$  100,000 / $\mu$ l.  

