## **8.0 RESPONSE ASSESSMENT / SAFETY AND QUALITY ASSURANCE**

### **8.1 Criteria for Response Assessment**

Subjects with measurable disease will be assessed by the RANO (radiographic assessment in neuro-oncology) criteria (Wen 2010). For the purposes of this study, subjects should be re-evaluated at the end of every 2 cycles (approximately every 8 weeks) with a contrast-enhanced cranial MRI scan. The response will be determined as outlined in the RANO criteria below.

*Measurable disease.* Bidimensionally, contrast-enhancing, measurable lesions with clearly defined margins by MRI scan, with a minimal diameter of 1 cm, and visible on 2 axial slices which are at least 5 mm apart with 0 mm skip. Measurement of tumor around a cyst or surgical cavity, if necessary, requires a minimum thickness of 3 mm. If there are too many measurable lesions to measure at each evaluation, the investigator must choose the largest two to be followed before a participant is entered on study. The remaining lesions will be considered non-measurable for the purpose of objective response determination. Unless progression is observed, objective response can only be determined when all measurable and non-measurable lesions are assessed.

Complete Response (requires all of the following):

- a) Complete disappearance of all enhancing measurable and non-measurable disease sustained for at least 4 weeks. In the absence of a confirming scan 4 weeks later, this scan will be considered only stable disease.
- b) No new lesions.
- c) All measurable and non-measurable lesions must be assessed using the same techniques as baseline.
- d) Subjects must be off corticosteroids (or on physiologic replacement doses only).
- e) Stable or improved non-enhancing (T2/FLAIR) lesions.
- f) Stable or improved clinically.

**Note:** Subjects with non-measurable disease cannot have a complete response. The best response possible is stable disease.

Partial Response (requires all of the following):

- a) Greater than or equal to 50% decrease compared to baseline in the sum of products of perpendicular diameters of all measurable enhancing lesions sustained for at least 4 weeks. In the absence of a confirming scan 4 weeks later, this scan will be considered only stable disease.
- b) No progression of non-measurable disease.
- c) No new lesions.
- d) All measurable and non-measurable lesions must be assessed using the same techniques as baseline.

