- e) The corticosteroid dose at the time of the scan evaluation should be no greater than the dose at time of baseline scan.
- f) Stable or improved non-enhancing (T2/FLAIR) lesions on same or lower dose of corticosteroids compared to baseline scan.
- g) Stable or improved clinically.

**Note:** Subjects with non-measurable disease cannot have a partial response. The best response possible is stable disease.

Stable Disease (requires all of the following):

- a) Does not qualify for CR, PR, or progression.
- b) The designation of stable disease requires a minimum of 4-week duration.
- c) All measurable and non-measurable sites must be assessed using the same techniques as baseline.
- d) Stable non-enhancing (T2/FLAIR) lesions on same or lower dose of corticosteroids compared to baseline scan. In the event that the corticosteroid dose was increased for new symptoms and signs without confirmation of disease progression on neuroimaging, and subsequent follow-up imaging shows that this increase in corticosteroids was required because of disease progression, the last scan considered to show stable disease will be the scan obtained when the corticosteroid dose was equivalent to the baseline dose.
- e) Stable clinically.

Progressive Disease (defined by any of the following):

- a)  $\geq 25\%$  increase in sum of the products of perpendicular diameters of enhancing lesions compared to the smallest tumor measurement obtained either at baseline (if no decrease) or best response, on stable or increasing doses of corticosteroids.\*
- b) Significant increase in T2/FLAIR non-enhancing lesion on stable or increasing doses of corticosteroids compared to baseline scan or best response following initiation of

therapy,\* not due to co-morbid events (radiation therapy, demyelination, ischemic injury, infection, seizures, postoperative changes, or other treatment effects).

- c) Any new lesion.
- d) Clear clinical deterioration not attributable to other causes apart from the tumor (e.g., seizures, medication adverse effects, complications of therapy, cerebrovascular events, infection, etc.) or changes in corticosteroid dose. The definition of clinical deterioration is left to the discretion of the treating physician, but it is recommended that a decrease in 20% of KPS or from any baseline to 50% or less be considered, unless attributable to comorbid events.
- e) Failure to return for evaluation due to death or deteriorating condition.

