- f) Clear progression of non-measurable disease.

\* Stable doses of corticosteroids include patients not on corticosteroids.

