### Sample size justification for primary endpoints:

Arm1: The Arm 1 study is to test the hypothesis that the combination treatment of TMZ and TRC102 will achieve 30% radiographic response rate (PR+CR) in patients with first recurrence of glioblastoma. A 2-stage design (minimax design) would discriminate between true response rates of no more than 13% and at least 30%. Maximum trial size would be set at 31 evaluable patients. If at least 7 responses (at least 22.5%) were observed among the 31 evaluable patients, this regimen would be considered worthy of further testing in this disease. If no more than 2 responses (no more than 10.5%) were observed among the initial 19 patients, the study would be terminated early and declared negative. This design yields at least 85% power to detect a true response rate of at least 30%. It yields at least .90 probability of a negative result if the true response rate is no more than 13%, with at least .54 probability of early negative stopping.

The Arm 2 study for bevacizumab-refractory patients is warranted only if the Arm 1 study meets its efficacy criteria. Arm 2 will not open without prior discussion between ABTC and CTEP.

Arm2: Arm 2 is a single arm study to test the hypothesis of clinical benefit of 30% radiographic response rate (PR+CR) for patients who had multiple numbers of prior therapies and are bevacizumab refractory, who are treated with TMZ and TRC102, and who continue bevacizumab. A safety run with 6 patients will be conducted prior to hypothesis testing in Arm 2. The expected DLT rate is  $\leq 33\%$ . If more than 2 patients experience dose limiting toxicity (DLT) associated with this regimen, Arm 2 will not be pursued further for safety reasons. If 2 or fewer patients experience DLT, Arm 2 will be

conducted using Simon's two-stage design. The 6 patients who were treated in the initial safe run will be counted as part of the first stage patients in the two-stage design.

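### Arm 2 admits patients without measurable disease, who under Section 8.1 cannot have the PR or CR that its primary endpoint counts

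*Combined protocol and SAP*

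**What the plan says.** Section 3.2, criterion 3, reads "Arm 1 patients must have measurable (defined by at least 1 cm x 1 cm) contrast-enhancing disease", shown on MRI within 21 days of starting treatment. It names Arm 1 only. For Arm 2, criterion 6 asks for progression on prior treatment: "Arm 2 patients must have progressed/recurred on bevacizumab as the most recent regimen". Criterion 4 and Section 4.2 require a baseline MRI of everyone, but not that it show measurable tumour: "All eligible patients who consent to this study must have a baseline (post-operative, if surgery is applicable) pre-treatment MRI".

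Section 11.0 describes Arm 2 as a "single arm study to test the hypothesis of clinical benefit of 30% radiographic response rate (PR+CR"). Its Simon two-stage rule stops at 2 or fewer responses in the first 18 patients and calls the regimen worth pursuing at 7 or more responses in 35. It states at least 90% power at a 30% response rate, a one-sided alpha of 0.05 against 10%, and a 73% chance of early stopping at 10%. Section 3.1 plans exactly 35 patients for Arm 2.

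Section 8.1 then fixes what a patient without measurable disease can achieve. Under complete response: "Subjects with non-measurable disease cannot have a complete response. The best response possible is stable disease". Under partial response: "Subjects with non-measurable disease cannot have a partial response. The best response possible is stable disease".

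**The concern.** Both arms have the same primary endpoint, but only Arm 1 has an entry rule ensuring that each patient can reach it. In Arm 2 a patient with no measurable lesion at baseline meets every visible criterion, takes one of the 35 places and cannot count as a response whatever the treatment does.

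The protocol itself shows how such patients can arise. Its list of progression events in Section 8.1 includes non-enhancing T2/FLAIR growth, clinical deterioration and "Clear progression of non-measurable disease". That list is written for on-study assessment, so it shows that entry without measurable disease is possible, not how often it will happen. The baseline scan may also follow surgery.

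The risk is a missed signal. Each counted patient who cannot respond pulls the observed rate down, which makes it more likely that Arm 2 stops after 18 patients or falls short of 7 responses while the combination is active in patients with tumour that can be measured. Section 11.0 does not say whether its 30% and 10% rates already allow for these patients.

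**Working it through.** **Inputs from Section 11.0.** Stage 1 has n1 = 18, and the arm continues only with 3 or more responses. Stage 2 adds 35 − 18 = 17 patients, and success is 7 or more responses in 35. The alternative rate is 0.30 and the null rate 0.10.

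**Formulas.** With X1 ~ Bin(18, p) and X2 ~ Bin(17, p):

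- P(stop at stage 1) = P(X1 ≤ 2)
- P(success) = Σ over x = 3 to 18 of P(X1 = x) × P(X2 ≥ 7 − x)

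**Reproducing the plan.**

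- At p = 0.30, P(stop) = 0.7^18 + 18(0.3)(0.7^17) + 153(0.09)(0.7^16) = 0.0016 + 0.0126 + 0.0458 = 0.060. Power is 0.9016.
- At p = 0.10, P(stop) = 0.7338 and alpha = 0.0474.

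All three stated figures hold: power of at least 90%, alpha within 0.05, and 73% early stopping. They are correct when the rate over all counted patients is 30% or 10%.

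**Adding patients who cannot respond.** Let m be the share of counted Arm 2 patients without measurable disease. The documents give no value, so every m below is an assumption. Take 30% and 10% as rates in measurable disease and count the others as non-responders, as the Section 8.1 notes imply. The overall rates become 0.30(1 − m) and 0.10(1 − m).

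| m (assumed) | Overall rate under the alternative | Power | P(stop at stage 1) | Type I error |
|---|---|---|---|---|
| 0 | 0.300 | 0.902 | 0.060 | 0.047 |
| 5% | 0.285 | 0.869 | 0.078 | 0.037 |
| 10% | 0.270 | 0.828 | 0.099 | 0.029 |
| 15% | 0.255 | 0.777 | 0.125 | 0.022 |
| 20% | 0.240 | 0.718 | 0.157 | 0.016 |

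**By number of patients.** Suppose k of the 35 cannot respond, placed at random across the 18 and the 17. One such patient gives 0.8786 if in stage 1 and 0.8917 if in stage 2. The average is (18/35)(0.8786) + (17/35)(0.8917) = 0.885. Two give 0.866 and four give 0.820.

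**Where 0.90 is lost.** Power equals 0.90 at an overall rate of 0.29918, so m = 1 − 0.29918/0.30 = 0.0027. That is 0.0027 × 35 ≈ 0.1 patient. Holding 0.90 would need a rate in measurable disease of 0.29918/(1 − m): 31.5% at m = 5%, 33.2% at 10% and 37.4% at 20%.

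**The case against.** The strongest reply rests on the word *evaluable*. The final Arm 2 rule counts 35 evaluable patients, and Section 8.1 opens with "Subjects with measurable disease will be assessed by the RANO (radiographic assessment in neuro-oncology) criteria". If evaluable means measurable at baseline, patients without measurable disease fall outside the count and power stays at 0.902. This reading is possible but less natural. The term is not defined, the stage-1 rule counts the initial 18 patients without that qualifier, and Section 8.1 gives these patients a response category instead of setting them aside. Section 3.1 plans exactly 35, which leaves no room for exclusions. Even on this reading the text needs changing.

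Second, Section 11.0 attaches the 30% to bevacizumab-refractory patients without restricting it to measurable disease. Read literally, 30% is the rate in whoever is enrolled, and the power statement is correct. That stands: the 90% is not an arithmetic error. But if so, the target for patients with measurable disease is higher than 30%, for example 0.30/0.90 = 33.3% at an assumed 10% share, and nothing in the plan says this was intended.

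Third, a two-stage design chosen to just meet its target always has little reserve. Arm 1 computes to 0.854 against a stated 85%. This is fair. The thin margin is not itself a fault. It only means that the design cannot absorb even one such patient and keep its stated power.

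Finally, the share is unknown and could be near zero, Type I error is safe, and Arm 2 may never open. These points limit the size of the problem. They do not remove the mismatch between who may enter and what is counted.

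**Conclusion.** The concern holds. As written, Arm 2 eligibility admits patients whom Section 8.1 bars from its primary endpoint. That conclusion rests on the text alone; the treatment schema figure was not available to check.

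The size of the effect is conditional. It assumes that 30% is the rate in measurable disease, that the other patients count as non-responders, and that their share is 5% to 20%. Power then falls from 0.902 to between 0.869 and 0.718, and the chance of a wrong stage-1 stop rises from 0.060 to between 0.078 and 0.157. There is no loss of power if the 30% was set for a mixed population or if no such patient is counted, but the plan establishes neither. The error runs one way, towards discarding an active regimen. This should be corrected before Arm 2 opens.

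**What to change.** Extend the baseline measurable-disease requirement in criterion 3 to the Arm 2 patients counted in the 18 and the 35. This must include the six safety run-in patients, because Section 11.0 counts them towards the first stage. If Arm 2 patients without measurable disease are still to be admitted and counted, say so in Section 11.0 and restate the Arm 2 power for the share expected. Use one unit, evaluable or initial patients, in both stages, and define it.

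The main change is one eligibility line. It adds no procedure, since every patient already has a pre-treatment MRI. Section 11.0 requires discussion between ABTC and CTEP before Arm 2 opens, so the change can precede any Arm 2 enrolment.

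The cost is a somewhat narrower population and slower accrual. Finding 35 patients with measurable disease takes 35/(1 − m) otherwise eligible patients: 36.8, 38.9 and 43.8 at assumed shares of 5%, 10% and 20%, or 37, 39 and 44 rounded up. The extra 2 to 9 patients amount to between 2/5 = 0.4 and 9/4 ≈ 2.3 months at the 4-5 patients per month in Section 3.1, a rate not stated separately for Arm 2.

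As a clerical matter of no weight here, the Planned Enrollment Report totals 51 while Section 3.1 plans 31 + 35 = 66. The same amendment could reconcile them.
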